### **3.0 Background\***

*3.1 Pediatric sickle cell disease (SCD) is a genetic disorder of the hemoglobin in which the course of acute pain from vaso-occlusion and its sequelae vary widely across genotypes and individual patients. SCD pain often begins during childhood and can progress to chronic pain for approximately 23% of children and adolescents. Youth with chronic SCD pain, that is pain that is present on most days per month and persists for at least 6 months, report high levels of functional disability, elevated depressive and anxiety symptoms, and reduced quality of life relative to youth with SCD without chronic pain. The complex, multifactorial nature of chronic SCD pain can also contribute to increased healthcare utilization for pain. The most effective management and treatment of chronic SCD pain likely requires individualized, multimodal, multidisciplinary treatments that go beyond pharmacological management alone. A range of evidence-based non-pharmacological treatments, such as behavioral health, complementary, and integrative health approaches, are recommended for chronic pain management and are gaining greater awareness and integration into comprehensive chronic pain care*

*3.2 Behavioral health treatment, such as cognitive-behavioral therapy (CBT) for pain, focuses on improved daily functioning and coping through several core treatment components such as psychoeducation about how the body processes pain, relaxation skills training, and cognitive strategies. CBT is effective for youth with a variety of chronic pain conditions, including chronic headache, recurrent abdominal pain, fibromyalgia, and recurrent sickle cell pain, in reducing pain intensity immediately following treatment and reducing pain-related*

*disability post-treatment and up to 12 months later9. CBT has been shown to reduce proinflammatory cytokines, including tumor necrosis factor- $\alpha$  (TNF- $\alpha$ ), C-reactive protein (CRP), interleukin-1 $\beta$  (IL-1  $\beta$ ), and interleukin-6 (IL-6), in adult patients with stroke, cardiovascular disease, cancer, depression, and anxiety. Interventions that reduce inflammation are especially needed for youth with SCD, for whom the propagation of inflammatory activity is a central mechanism that triggers vaso-occlusive episodes and long-term disease complications, such as organ damage. The few existing randomized clinical trials (RCTs) of CBT for acute or recurrent SCD pain in pediatrics are primarily limited by small sample sizes, poor treatment engagement, and inadequate randomization, stratification, or blinding; further, no clinical trials have yet to specifically target chronic SCD pain10.*

**3.3** *Youth with chronic SCD pain need an evidence-based, culturally informed, adaptive treatment. Behavioral treatments that are tailored to patient and family needs are beneficial when patients may require different levels of care11. Tailored or adaptive treatments align with a stepped care model that moves from lower (screening) to higher (intervention) levels of care in a cost-effective manner12. Adaptive treatments have been successful for a variety of pediatric chronic conditions, such as asthma13, depression14, anxiety15, and adults with chronic pain and co-morbid psychological disorders16-18. Adaptive designs are more effective in improving health outcomes, satisfaction with treatment, and reducing healthcare use than standard protocols where patients receive a fixed “one size fits all” treatment that is not personalized to their needs; adaptive designs are also recommended for tailoring evidence-based interventions with culturally diverse populations19-21. Adaptive treatments can integrate evidence-based strategies to address common co-morbid problems associated with chronic pain, such as elevated anxiety or depressive symptoms or sleep disturbance14,16,22,23. Teaching parents problem-solving skills can reduce caregiver stress among families managing chronic pain and illness13,24,25.*

**3.4** *We will utilize an adaptive behavioral treatment to target psychosocial risk factors for youth with chronic SCD pain as a first step towards developing a stepped care model for SCD pain. The proposed treatment, called Back2Life, is innovative because it is culturally informed by families’ and patients’ feedback regarding their treatment preferences and targets psychological co-morbidities that are often excluded in clinical trials. The overarching hypothesis driving the proposed intervention is that disrupting the complex interacting psychosocial factors that can exacerbate chronic SCD pain will prevent and/or reduce poor health outcomes in children and adolescents with SCD.*

## **4.0 Study Endpoints\***

**4.1** *Primary study endpoints include markers of treatment feasibility, acceptability, and preliminary efficacy related to pain interference, pain characteristics (burden, intensity, frequency), and pain coping efficacy. Secondary*

*outcomes will include healthcare use for pain (admissions, ED visits, opioid use) and inflammatory biomarkers (e.g., proinflammatory cytokines).*

## **5.0 Study Intervention / Design**

*A proof-of-concept trial is a cost-effective method to determine if the treatment package can achieve a clinically significant improvement in outcome in a small, select sample. As a single-arm trial, a proof-of-concept determines whether the treatment merits rigorous and costly testing using an RCT or requires further optimization, thereby minimizing waste of resources and first ensuring clinically significant improvements can be achieved under optimum conditions.*

*A manualized treatment protocol, including intervention content, delivery style, and materials were adapted for optimization based on analyses of qualitative feedback from qualitative interviews and theater testing (i.e., pre-testing the intervention with the target audience to examine attitudes towards the format, content, etc). The treatment program includes 6-sessions of standard treatment (delivered to all participants) and 1-4 tailored sessions to address common co-morbidities associated with chronic pain (sessions assigned based on results of baseline assessment). The treatment manual leverages existing evidence-based interventions into a treatment package that will be tailored to individual patient and family needs.*

## **6.0 Procedures Involved\***

**6.1** *Patients and parents who provide consent/assent will participate for 8 months (between 12-17 study visits). The study involves a combination of 1) assessments (4 study visits), 2) treatment sessions (6-10 study visits), 3) booster sessions (1 study visit), and 4) a qualitative interview (combined with a post-treatment assessment).*

**6.2** *Baseline Assessment: Parents and teens will complete an assessment of surveys at a baseline study visit. We will ask parents and teens to complete brief questionnaires about the teen's pain, sleep, mood, physical functioning, and interest in participating in the program (see Measures below). Parents will also complete a brief questionnaire about stress related to parenting. Teens will complete a 1-week daily diary to record pain ratings, school attendance, sleep quality, and medication use.*

**6.3** *Treatment Program: All teens will receive the standard 6-session pain coping skills training program (learning ways to cope with and manage chronic sickle cell pain). The standard program includes topics that were identified by teens with chronic sickle cell pain and their parents as important skills for all teens with chronic pain and sickle cell disease. Research staff will use the information from the baseline assessment to tailor the treatment program to the needs of each teen and family. In addition to the standard 6-session program,*

*teens may receive an additional 1 to 4 sessions that may help with specific problems and/or co-morbidities related to pain. For example, additional sessions may include topics such as difficulty sleeping, bad moods, or parenting stress. Patients and parents who do not screen into the additional tailored sessions based on their baseline assessment scores will still have the option to participate in any of the additional sessions. Please see Appendix A for Back2Life Treatment Session Overview.*

**6.4 Treatment Sessions:** The treatment sessions will be conducted in-person at a CHOA hospital campus or via telehealth using HIPPA-compliant platform (e.g., Zoom). An in-person study visit for the first treatment session is strongly encouraged to promote optimal therapeutic rapport, and all remaining treatment sessions may be conducted in-person or via telehealth, based on patient/family preference. Treatment sessions will begin 1 week following the completion of baseline assessment. Each session will last about 1 hour, once a week. A treatment session window of +/- 14 days will allow flexibility to support adherence. Each session will focus on teaching a new skill or strategy to improve chronic pain management. Sessions will be led by a psychology provider (PhD student, post-doctoral fellow, psychologist). Teens will be asked to practice the coping skills at home between sessions and keep a brief diary of their practice, pain symptoms, school attendance, and medication use. At least one parent or guardian is required to attend with their teen. However, all interested family members (parents, grandparents, siblings) are encouraged to attend sessions with their teen. Parents will also receive education and training in the skills their teen will be learning along with behavior management strategies to support teen's use of skills at home. One booster session will be offered 2 months after completing the program. The booster session will focus on problem-solving any difficulties teens or parents may have had with using the skills at home or school. The booster session will be conducted either in-person, telehealth, or by phone, depending on family preference. Intervention content will be sensitive to developmental differences. For example, parents of school-aged children will be guided to coach their children's use of coping strategies. Parents of adolescents will be guided to provide monitoring and oversight of adolescent self-management and communication with providers to promote independence. Sessions may be audio recorded and will only be reviewed by research staff to make sure that the content of the training program is being provided accurately and thoroughly to all participants. Between sessions, follow-up by phone or during inpatient admissions will allow for opportunities to problem-solve integration of strategies. Make-up sessions will be built into the treatment session timeline to allow flexibility and treatment adherence.

**6.5 Follow-Up Assessments:** All teens and parents will complete the same assessment of surveys after completing the standard 6-session program (post-treatment evaluation). Parents will also report on any changes to their teen's medical treatment plan since the last assessment. All teens and parents will

*complete the assessments at 3-months and 6-months follow-up from baseline. All assessments can be completed in-person, at home using online or paper-and-pencil questionnaires, or by telehealth (video or phone) depending on teen and parent preference. An assessment window of +/- 2 weeks will allow flexibility to support recruitment and adherence.*

**6.6 Blood Sample Collection:** *As an optional component of the study, all teens will have the option to consent to blood sample collection at three assessment visits: baseline, 3-month follow, and 6-month follow-up. Blood sample collection will occur at or close to each time point allowing at least 2 weeks following an acute care visit for pain to ensure steady disease state collection. To enhance clinical implementation and acceptability, efforts will be made to coordinate blood sample collection during routine medical visits to minimize blood draws. Each sample will be about 4 teaspoons (about 20 milliliters) of blood, which will be drawn in the clinic or hospital, and will only take a few seconds. Collected blood samples will be immediately transported to [name] laboratory for labeling, processing, storage, and analysis.*

**6.7 Qualitative Interview:** *At the end of the treatment program, parents and teens will be asked for feedback in a one-on-one interview lasting about 30 minutes. Feedback may include how they liked the program, what they thought about the content of the program, and any suggestions or changes to the materials or format. Information from these interviews will be used to refine and modify the Back2Life program. Interviews can be conducted in-person or by telehealth (video and/or phone). Interviews will be audio recorded as digital files and transcribed for analysis by advanced psychology PhD students or trained study members. Audio recordings will be saved for up to 6 years following completion of the study and saved via password-protected computer that is only accessible to the PI to ensure security. No audio recordings will be used for educational or presentation purposes. The research design does not require subjects to be deceived.*

**6.8 Intervention fidelity.** *Written intervention manuals will promote quality assurance and include materials for training, supervision, and fidelity monitoring. All sessions may be audio recorded; a random sampling of 25% of sessions from each family will be reviewed with mentors to monitor protocol adherence. Fidelity checklists will be completed independently by 2 reviewers (PhD students). Participant homework completion will be routinely assessed.*

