## 1.0 Study Summary

Study Title	Building Adaptive Coping and Knowledge to Improve Daily Life (Back2Life): A Pilot Feasibility Clinical Trial for Youth with Chronic Sickle Cell Pain
Study Design	Single-Arm, Uncontrolled Behavioral Clinical Trial
Primary Objective	Conduct a pilot proof-of-concept clinical trial to evaluate the feasibility, acceptability, and preliminary efficacy of Back2Life with youth with chronic SCD pain and their parents
Secondary Objective(s)	Refine intervention content and delivery based on participant qualitative feedback; Evaluate a biological response to intervention
Research Intervention(s)/Interactions	The treatment program includes 6-sessions of standard cognitive-behavioral therapy (CBT) treatment (delivered to all participants) and 1-4 tailored sessions to address common co-morbidities associated with chronic pain (sessions assigned based on results of baseline assessment). The treatment manual leverages existing evidence-based interventions into a treatment package that will be tailored to individual patient and family needs.
Study Population	Children with sickle cell disease (SCD) aged 10-18 years old and their parent(s)
Sample Size	25 parent-child dyads
Study Duration for individual participants	8 months
Study Specific Abbreviations/ Definitions	Back2Life: Building Adaptive Coping and Knowledge To improve daily Life CBT: cognitive-behavioral therapy
Funding Source (if any)	NHLBI

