## **14.0 Withdrawal of Participants\***

- 14.1** Participants have the right to leave the study at any time without penalty. If participants choose to go off the study treatment or leave the study before the final planned study visit, participants may be asked to have some final study procedures completed including but not limited to follow-up surveys at the planned end of the program, and follow-up surveys at 3-months and 6-months after the program.
- 14.2** Study personnel may stop participant involvement in the study without participant consent for any reason to maintain the best interest of the participant or if participants object to any future changes that may be made in the study plan.

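### The main schedule (6.5) times the 3- and 6-month assessments from baseline, but the withdrawal text (14.1) times them from the end of the program, about 42 to 70 days later

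*Combined protocol and SAP*

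**What the plan says.** Section 6.5 is the schedule for all participants. After the post-treatment evaluation, teens and parents "complete the assessments at 3-months and 6-months follow-up from baseline". It adds: "An assessment window of +/- 2 weeks will allow flexibility to support recruitment and adherence".

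Section 14.1 covers people who stop treatment or leave the study early. It says that they may be asked for surveys at the planned end of the program, and then for "follow-up surveys at 3-months and 6-months after the program".

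The row "Study Duration for individual participants" in 1.0 gives 8 months, and 6.1 and 9.1 repeat that figure. On treatment timing, 6.4 says: "Treatment sessions will begin 1 week following the completion of baseline assessment". Sessions are weekly, and 6.1 allows 6 to 10 of them. A booster is offered two months after the program.

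The end of the program is not defined. Section 5.0 counts the tailored sessions as part of it: "The treatment program includes 6-sessions of standard treatment (delivered to all participants) and 1-4 tailored sessions to address common co-morbidities". Section 6.5, however, ties the post-treatment evaluation to the standard six sessions alone.

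Hypothesis 2 (2.3) and 17.4 refer to the follow-up time points without naming an anchor.

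**The concern.** The same two labels, 3-month and 6-month, have two starting dates in current text. If both sections are followed as written, an early leaver's 6-month survey comes about 6 to 10 weeks later than a completer's, and both enter the data under one name.

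The labels also carry the efficacy result. Section 17.4 reports effect sizes at 3 and 6 months, and Hypothesis 2 is stated at 6 months. On the baseline anchor, 6 months is the time since baseline, and the time since treatment is shorter and depends on how many sessions a teen received. On the program anchor, 6 months is the time since the program ended. The two answer different questions about how long any benefit lasts, which matters for a pilot meant to inform a later controlled trial.

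**Working it through.** **Inputs.** Day 0 is completion of the baseline assessment. The first session is on day 7 and sessions are weekly (6.4). The number of sessions is k = 6 to 10 (6.1). The session window is ±14 days (6.4) and the assessment window is ±14 days (6.5). The booster comes 2 months after the program (6.4). Assumption: 1 month = 365.25/12 = 30.44 days, so 2, 3, 6 and 8 months are 61, 91, 183 and 243.5 days.

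**Last session.** L = 7 + 7(k − 1) = 7k, which is day 42 for k = 6 and day 70 for k = 10.

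**The plan's own figure, 8 months (day 243.5).**
- Baseline anchor: the last visit is on day 183, and 183/30.44 = 6.0 months. With the full window, (183 + 14)/30.44 = 6.5 months.
- Program anchor (all sessions): the last visit is on day 42 + 183 = 225 to 70 + 183 = 253, which is 7.4 to 8.3 months.
- The 8 months lies inside the second range and beyond the first. To reach it on the baseline anchor, 243.5 − 183 = 60.5 further days are needed, or 243.5 − 197 = 46.5 with the full window.

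**Visit timing under each anchor.**

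| | From baseline (6.5) | From last session (14.1) |
|---|---|---|
| 3-month visit | day 91 | 42 + 91 = 133 to 70 + 91 = 161 |
| Days since last session | 91 − 42 = 49 to 91 − 70 = 21 | 91 |
| 6-month visit | day 183 | 225 to 253 |
| Days since last session | 183 − 42 = 141 to 183 − 70 = 113 | 183 |

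Under 6.5, therefore, the 6-month visit falls 113/30.44 = 3.7 to 141/30.44 = 4.6 months after the last session.

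**Shift between anchors.** The shift equals L: 42 to 70 days, or 42/14 = 3 to 70/14 = 5 assessment windows. Other readings:
- If baseline means the visit and the one-week diary in 6.2 follows it, the first session is on day 14 and the last on 14 + 7(k − 1) = day 49 to 77. The shift is then 49 to 77 days.
- If the program means only the standard six, delivered first, the shift is 42 days for everyone.
- If the last session moves by its ±14-day window, the shift is 42 − 14 = 28 to 70 + 14 = 84 days. Make-up sessions could lengthen it further.

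**Booster.** Its nominal date is L + 61 = day 103 to 131. A baseline-anchored 3-month visit on day 91 precedes it by 12 to 40 days. A program-anchored visit follows it by (L + 91) − (L + 61) = 30 days. The order is nominal: with 6 sessions, a visit at the end of its window (91 + 14 = day 105) passes the booster (day 103). The baseline-anchored 6-month visit follows the booster by 183 − 103 = 80 to 183 − 131 = 52 days.

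**The case against.** The two sections do not have equal weight. Section 6.5 is the schedule and binds everyone. Section 14.1 is conditional text on withdrawal. A reader might infer two rival schedules and conclude that the timing of the efficacy results cannot be known. The documents do not support that, because 6.5 gives an explicit anchor, and on that reading the main defect is the wording of 14.1. What remains is that 14.1, if applied, times the same-labelled surveys differently, and that the stated duration does not match 6.5.

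A reader might also take the 8 months as proof that the program anchor was intended. It is not proof. The time from consent to baseline is not given. The one-week diaries (6.13) and blood draws deferred until at least two weeks after acute pain care (6.6) could also add time. None of these is shown to fill the 47 to 61 days needed, but none is ruled out.

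Finally, the analysis is exploratory (17.5) in a single-arm pilot. No test, effect-size formula or power figure changes, so this is a point of consistency and interpretation.

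**Conclusion.** The inconsistency stands. Section 6.5 sets the visits from baseline for everyone, 14.1 sets the same-labelled surveys from the end of the program, and no section reconciles them. Nominally the anchors are 42 to 70 days apart (49 to 77 if the diary week comes after day 0), at least three times the assessment window. This assumes weekly sessions on schedule; the session window alone widens the range to 28 to 84 days, so the figures are not exact.

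Taking 6.5 as controlling, the 6-month result applies about 4 to 5 months after the last session, and the 3-month visit nominally comes before the booster. It would be tempting to extend the booster point to Hypothesis 2, but nominally the 6-month visit follows the booster on either anchor. Nor do the documents show that pain scores are biased by the choice. The mismatch with the stated 8 months is supporting evidence only.

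**What to change.** Use one anchor for the 3- and 6-month assessments for all participants, including early leavers.

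- **If baseline is kept:** change 14.1 to time the surveys from baseline. Correct the 8 months in 1.0, 6.1 and 9.1, or state what fills the extra time. Describe the 3- and 6-month results in 17.4 as time from baseline.
- **If the program anchor is intended:** change 6.5, and define program end as the last scheduled session, standard or tailored, using its planned date for early leavers.

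In either case, carry the anchor into 2.3, 2.4, 2.5, 6.6 and 17.4. State that the 6- and 12-month healthcare-use windows in 6.13 run from treatment, because 2.4 reports healthcare use under the 6-month follow-up label. Report actual days from baseline and from the last session for each assessment.

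The cost is wording in these sections and two derived day counts per assessment, with no added visits. Choosing the program anchor would move follow-up visits about 6 to 10 weeks later than 6.5 now implies.

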## 2.0 Objectives\*

**2.1 Primary Aim:** Conduct a pilot proof-of-concept clinical trial to evaluate the feasibility, acceptability, and preliminary efficacy of Back2Life with youth with chronic SCD pain and their parents (n=25). We will use an adaptive treatment approach with 6-10 module-based treatment sessions selected on the

basis of baseline assessment (rather than a fixed treatment approach) to allow flexibility in tailoring treatment components to meet individual family needs.

*2.2 Hypothesis 1: It is expected that the Back2Life treatment program will be feasible and acceptable as demonstrated by high levels of treatment engagement ( $\geq 80\%$  attendance of treatment sessions) and high ratings of treatment satisfaction.*

*2.3 Hypothesis 2: Participants who complete the Back2Life treatment program will report reductions in pain interference and pain symptoms (intensity and frequency) at post-treatment and 6-month follow-up. Preliminary efficacy will be defined as clinically significant ( $\geq 30\%$ ) reductions in pain interference and pain.*

*2.4 Exploratory hypothesis 1: We will explore reductions in secondary outcomes related to healthcare use for pain (inpatient hospitalizations, ED visits, and opioid use) at 6-month follow-up.*

*2.5 Exploratory hypothesis 2: The Back2Life treatment program will result in measurable reductions in inflammatory biomarkers from baseline to 3-month and 6-month follow-up.*

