#### 6.13 Secondary Treatment Outcomes

1) *Healthcare utilization will be extracted from the medical record to document the total number of emergency department (ED) visits and admissions for pain for 6-months and 12-months pre- and post-treatment.*

2) *Opioid use will be calculated based on participant completion of daily diaries for 1-week at each assessment visit. Participants will record opioid use daily (presence/absence). Opioid use also will be documented on daily diaries throughout the course of treatment.*

3) *Inflammatory biomarkers, including but not limited to, proinflammatory cytokines and markers, such as interleukin -18 (IL-18), interleukin – 6 (IL-6), interleukin – 8 (IL-8), tumor necrosis factor – alpha (TNF- $\alpha$ ), c-reactive protein (CRP), brain-derived neurotrophic factor (BDNP), and interferon gamma (INF- $\gamma$ ) will be analyzed. Plasma concentrations for each biomarker will be determined by a custom multiplex kit (e.g., FirePlex-384 Multiplex Assay by abcam), an immunoassay panel detected by flow cytometry used for simultaneous quantitative measurement in a single sample with high sensitivity and high throughput capacity. All samples will be analyzed in triplicate.*

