## 10.0 Subject Population\*

10.1 *Inclusion Criteria: Youth will be eligible for inclusion if they are (a) 10-18 years old, (b) diagnosed with SCD (any genotype), (c) report chronic pain, (d) speak and read English, and (e) have not initiated new disease modifying-treatments (e.g. hydroxyurea, Endari, voxeletor, crizanlizumab, chronic transfusions) or significantly increased dosages (mg/kg) of any disease-modifying treatments in the past 3 months. As in our prior work, chronic pain classification will be based on pain frequency and persistence: 1) patient reports  $\geq 12$  pain days per month, and 2) pain frequency persisted for  $\geq 3$  months. Parents or caregivers will be eligible if they speak and read English.*

10.2 *Exclusion Criteria: Youth will be excluded if they (a) have comorbid medical conditions typically associated with pain but unrelated to SCD (e.g., rheumatologic disorders or inflammatory bowel disease); (b) are receiving chronic transfusion indicated for central nervous system risks and/or complications, previous overt strokes, or significant cognitive or developmental limitations, as per their healthcare provider or parent, that would impair completion of self-report measures or engagement in treatment sessions; and (d) received  $\geq 3$  sessions of outpatient psychological therapy for pain management in the 6 months prior to screening to ensure inclusion of patients and families who are naïve to CBT for pain. Parents or caregivers will be excluded if they have significant cognitive limitations or severe psychiatric conditions, as per the child's healthcare team or history, that would impair completion of self-report measures or engagement in treatment sessions.*

10.3 *25 child-parent dyads will be recruited from CHOA SCD clinics. Participants will include parents and children with SCD aged 10-18, which represents the developmental period when chronic pain is prevalent among youth. Patients who are 18 years old may participate without a parent or caregiver, although parent participation is preferred.*

10.4 *Community Participation (if applicable)*

- N/A

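### The steady-state rule for blood draws reacts only to acute care visits for pain, so samples taken soon after other acute illness or a home-managed crisis can enter the biomarker comparison

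*Combined protocol and SAP*

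**What the plan says.** Section 6.6 offers teens optional blood sampling at baseline, 3 months and 6 months. Draws happen at or near each time point, "allowing at least 2 weeks following an acute care visit for pain to ensure steady disease state collection", and are fitted around routine medical visits where possible. No other clinical condition for a draw is given.

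The samples serve Exploratory hypothesis 2 (Section 2.5), which predicts "measurable reductions in inflammatory biomarkers from baseline to 3-month and 6-month follow-up". The panel in Section 6.13 includes CRP, IL-6 and TNF-alpha. Section 1.0 lists the biological response as a secondary objective and describes a single-arm, uncontrolled trial.

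The events that trigger the wait are also outcomes. Section 2.4 explores reductions in "secondary outcomes related to healthcare use for pain (inpatient hospitalizations, ED visits, and opioid use) at 6-month follow-up", and Section 6.13 uses the medical record "to document the total number of emergency department (ED) visits and admissions for pain".

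Two further passages bear on the point. Section 3.2 states that in this disease "the propagation of inflammatory activity is a central mechanism that triggers vaso-occlusive episodes and long-term disease complications". Under Section 10.1, "chronic pain classification will be based on pain frequency and persistence", with a threshold of at least 12 pain days a month for at least 3 months.

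**The concern.** Section 6.6 accepts that the samples must be taken at steady state and claims that the interval secures this. But the interval is set by one kind of care-seeking, not by the teen's condition. A teen recently treated for fever or infection, or one who has just come through a crisis at home, meets the rule as written. With at least 12 pain days a month at entry, the absence of a visit says little about the two weeks before the draw.

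What is at stake is the within-person change in inflammatory markers. Unscreened samples make that change noisier. If their share differs between baseline and follow-up, they also shift its mean. Because the trigger is an event whose frequency the study hopes to change, equal shares cannot be taken for granted. With no control arm, nothing in the design would reveal the difference.

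**Working it through.** **1. Is the gap closed elsewhere?**

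- Section 6.13 (biomarker measure) gives the analytes and the assay, with no rule on the teen's state at the draw.
- Section 10.2 excludes comorbid painful conditions unrelated to sickle cell disease, with rheumatologic disorders and inflammatory bowel disease as examples. That acts at enrolment and does not cover acute illness at a draw.
- Section 17.4 names age, number of sessions and treatment changes as example covariates. Clinical state at the draw is not among them.
- Section 18.0 covers oversight of the blood analysis, with no check on disease state.
- Sections 6.2 and 6.13 describe a 1-week diary at each assessment, recording pain ratings and medication use among other items. It is not linked to the draw and spans 7 of the 14 days.

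The gap is not closed.

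**2. The plan's own power figure.** No power or effect size is given for biomarkers. The only figure, in Section 17.5, is for pain: d = 0.55, n = 25, about 80%. Alpha is not stated; I assume 0.05 two-sided. The normal approximation gives Φ(0.55 × √25 − 1.96) = Φ(0.79) = 78.5%, which agrees. The exact paired t-test gives 75.1%, and I use that as the base below. Applying d = 0.55 to a biomarker is an assumption.

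**3. What unscreened samples could do (all inputs assumed).** Let D be the rise in the log marker in an affected sample, in SD units. Let q0 and q1 be the affected shares at baseline and follow-up. Assume the steady-state change has SD 1, affected status is independent across time points, and all 25 teens opt in.

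- False shift in mean change = (q1 − q0) × D
- Added variance of the change = D² × [q0(1 − q0) + q1(1 − q1)]
- Observed d = (0.55 − false shift) / √(1 + added variance)

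Example with q0 = q1 = 20% and D = 1: added variance = 0.16 + 0.16 = 0.32, and observed d = 0.55/√1.32 = 0.48.

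| q0 → q1 | D | False shift (SD) | Observed d | Power, n = 25 |
|---|---|---|---|---|
| 20% → 20% | 0.5 / 1.0 / 1.5 | 0 / 0 / 0 | 0.53 / 0.48 / 0.42 | 72% / 63% / 52% |
| 20% → 40% | 0.5 / 1.0 / 1.5 | +0.10 / +0.20 / +0.30 | 0.43 / 0.30 / 0.18 | 54% / 30% / 14% |
| 20% → 10% | 0.5 / 1.0 / 1.5 | −0.05 / −0.10 / −0.15 | 0.58 / 0.58 / 0.56 | 80% / 80% / 77% |

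Equal shares cost precision only. A rising share hides a real fall. A falling share creates a false one, so the apparently good power in the last row is partly artefact.

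**4. Timing at baseline.** Section 6.4 starts treatment 1 week after the baseline assessment. For a visit v days before that assessment, the earliest permitted draw is day 14 − v. For v of 7 or less, that is day 7 or later, at or after the first scheduled session. The current rule already allows this. A wider trigger would make it more common.

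**The case against.** **Direction.** A reader might infer that the filter must weaken over time: the program teaches coping at home, visits fall, fewer crises trigger the wait, and follow-up values are pushed up. The documents do not support this. Section 2.4 only explores reductions in visits, and no passage says that crises move from hospital to home. Section 2.3 hypothesises less pain, so visits could fall because crises fall.

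The sign turns on that choice. Assume 1 crisis per 30 days, Poisson, with the share leading to a visit falling from 50% to 25%. The share of samples within 14 days of an unscreened crisis at baseline is 1 − exp(−0.50 × 14/30) = 20.8%. At follow-up it is:

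- crises unchanged: 1 − exp(−0.75 × 14/30) = 29.5%
- crises down 30%: 1 − exp(−0.7 × 0.75 × 14/30) = 21.7%
- crises down by a third: 20.8%, no difference
- crises down by half: 1 − exp(−0.5 × 0.75 × 14/30) = 16.1%, the opposite sign

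**Size.** The documents give no crisis rate, visit share or marker elevation. Section 3.2 says that inflammation triggers crises. It does not say that a home-managed crisis raises these markers for two weeks. This part of the objection stands too.

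**Other inferences.** A reader might add that transfusion timing is uncontrolled, but nothing in the documents says that transfusion alters these markers. A reader might also count the two weeks from arrival. That reading is strained, since it would defeat the rule's stated purpose.

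**Deferral is unworkable.** In teens with at least 12 pain days a month, nothing in the plan separates a crisis from an ordinary pain day. At the assumed one crisis a month, only exp(−14/30) = 63% of nominal dates are clear, so 37% of draws would be deferred or flagged. All three dates are clear in exp(−3 × 14/30) = 25%, about 6 of 25 teens. This stands, and the fix does not defer for home-managed pain.

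**Staff and existing records would cope.** The purpose clause and the steering to routine visits may keep obviously ill teens from being drawn, and charts and diaries could be searched afterwards. This stands only in part. A purpose is not a rule. The chart shows care contacts, not home crises, and the assessment diary covers only half the interval.

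**Conclusion.** The concern holds in limited form. The rule in Section 6.6 does not by itself deliver the steady state it promises, because acute care for other causes and home-managed crises fall outside it. Samples not at steady state can therefore enter the comparison; how many do is unknown.

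The documents do not fix the direction or size of a bias. Under the assumptions shown, equal shares of 20% reduce power at 25 pairs from 75% to between 52% and 72%. Unequal shares shift the mean change by 0.05 to 0.30 SD, either way. These are illustrations, not estimates, and they assume full opt-in. With 15 pairs, power is already 51% before any contamination.

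A reader might infer that the trial's main conclusions are at risk. They are not: feasibility, acceptability and the pain outcomes do not use these samples. The issue bears only on how an opt-in, exploratory biomarker result is read, so it is minor.

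**What to change.** - **Section 6.6, trigger.** Apply the 2-week interval to any acute care visit or admission, for any cause, counted from discharge.
- **Section 6.6, record at each draw.** Note the date, the days since the last acute care contact, any recent fever or infection, and any home-managed crisis. Use a short 14-day recall question plus a chart check. State a working definition that separates a crisis from an ordinary chronic-pain day.
- **Flag rather than defer.** Do not postpone draws for home-managed pain. Flag those samples, any draw taken inside the interval, and any baseline draw taken after the first treatment session.
- **Section 17.4.** Report the biomarker change with and without flagged samples.

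The cost is some wording, a few items on the sample form and one sensitivity analysis. A few draws will be postponed, and some baseline draws may fall near or after the first session. The sensitivity analysis will use fewer samples. For example, if 0.5 home-managed crises per 30 days is assumed at both time points, exp(−2 × 0.5 × 14/30) = 63% of pairs are free of that flag, about 16 of 25 if everyone opts in.
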